		Day 1	Week 4	Week 8	Week 16	Week 24	Week 36	Week 44	Week 52		1 Wee k 54	2 Week 56	 If a participant ends study treatment prior to Week 52, the ET visit assessments should be performed within 1 week of the last dose of study treatment unless participant is discontinued due to the results of first dose cardiac monitoring when ET visit should occur within 3 calendar days (see Section 10.10.3). Due to first dose cardiac monitoring, the Day 1 visit should be conducted in the morning and not on a Friday or the day before a site observed holiday. See Section 10.10.3. The SFU 1 and SFU 2 Visits are to be conducted 2 and 4 weeks (± 3 days) after last dose of study treatment, respectively. Home health and/or telehealth visits may apply for certain extenuating circumstances only. See Section 8.1.2 and Section 8.1.3.
Study Day	-28 to -	1	29	57	113	169	253	309	365				Day relative to start of study intervention (Day 1).
Visit Window (±days)	NA	NA	(±5)	(±5)	(±5)	(±7)	(±7)	(±7)	(±7)		(±3)	(±3)	 All screening should be done ≤28 days before the first dose. See Section 8.4.3 for follow-up AE and SAE assessments.
Prior/concomitant treatment(s)	X	X	X	X	X	X	X	X	X	X	X	X	See Section 6.9 for additional information
Confirm daily use of emollient/moisturizers		X	X	X	X	X	X	X	X	X			Participants must apply topical emollient or moisturizer at least once daily for ≥1 week prior to Day 1 and continue daily application over the course of the study without change. On visit days during the study, participants should not apply any topical emollient or moisturizer until the study visit has been completed.
Assess treatment continuation criteria					X								Participants who do not meet the pre-specified continuation criteria (EASI-50) will be discontinued at Week 16 and will complete ET visit procedures. Refer to Section 7.1.5 of the protocol for details.

Visit Identifier Abbreviations used in this table may be found in Appendix 12	Screen					ent Per				ET		fety ow-up	Notes

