		Day 1	Week 4	Week 8	Week 16	Week 24	Week 36	Week 44	Week 52		1 Wee k 54	2 Week 56	 If a participant ends study treatment prior to Week 52, the ET visit assessments should be performed within 1 week of the last dose of study treatment unless participant is discontinued due to the results of first dose cardiac monitoring when ET visit should occur within 3 calendar days (see Section 10.10.3). Due to first dose cardiac monitoring, the Day 1 visit should be conducted in the morning and not on a Friday or the day before a site observed holiday. See Section 10.10.3. The SFU 1 and SFU 2 Visits are to be conducted 2 and 4 weeks (± 3 days) after last dose of study treatment, respectively. Home health and/or telehealth visits may apply for certain extenuating circumstances only. See Section 8.1.2 and Section 8.1.3.
Study Day	-28 to -	1	29	57	113	169	253	309	365				Day relative to start of study intervention (Day 1).
Visit Window (±days)	NA	NA	(±5)	(±5)	(±5)	(±7)	(±7)	(±7)	(±7)		(±3)	(±3)	 All screening should be done ≤28 days before the first dose. See Section 8.4.3 for follow-up AE and SAE assessments.
Assessments													• See Section 8 for additional information.
Efficacy													• See Section 8.2 for additional information.
EASI, IGA, BSA affected by AD	X	X	X	X	X	X	X	X	X	X		X	
PP-NRS, Skin pain NRS		X	X	X	X	X	X	X	X	X		X	All PROs and AD clinical assessments should be completed prior to other clinical activities and investigative product administration.
POEM		X				X			X	X			All PROs and AD clinical assessments should be completed prior to other clinical activities and investigative product administration
Safety													• See Section 8.3 for additional information.
Serious and nonserious AE monitoring	X	X	X	X	X	X	X	X	X	X	X	X	• See Section 8.4 for additional information.

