7.1.5. Lack of Efficacy

Lack of efficacy will result in permanent discontinuation of study intervention only for the reason below:

 Participants who do not meet EASI-50 criteria at Week 32 in Part 1 (Week 16 of OLE) or at Week 16 of Part 2. In the case of lack of efficacy, the participant will be permanently withdrawn from administration of study intervention, complete Early Termination procedures, and then complete the 2- week (SFU 1) and 4-week (SFU 2) follow-up visits.

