In Part 1 OLE phase, since no estimands are defined for (binary or continuous) efficacy endpoints, all observed data collected/assessed regardless of any prior intercurrent events will be included in deriving the efficacy endpoints at a visit. If the binary efficacy endpoint at any visit has missing value, it will be handled by setting the binary efficacy endpoint to non-response. This method of handling missing binary efficacy endpoint is known as missing response as non-response (MR=NR), which is similar to using Estimand E1a (treatment policy estimand). If the continuous efficacy endpoint at any visit has missing, it will remain as missing, without imputation of missing value at this visit, which is similar to using Estimand E2a (treatment policy estimand). The same approach of including all observed data collected/assessed regardless of any prior intercurrent events will also be applicable to Part 2 OL Safety phase. Missing binary efficacy endpoints in Part 2 OL Safety phase will not be imputed as non-response, only observed values will be summarized.

In general, missing values in any (binary or continuous) efficacy endpoint will not be imputed when summarizing these endpoints using descriptive statistics. In addition, missing values for safety endpoints will not be imputed.

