Appendix 2. Data Derivation Details

Appendix 2.1. Definition and Use of Analysis Visit Windows in Reporting

There are two sets of analysis visit windows, one set for Part 1 (both DB and OLE phases) and another set for Part 2 (OL). For reporting purposes, the analysis visit windows will be used for efficacy and safety display that show by scheduled visits. Observations from all visits including scheduled, unscheduled and early termination visits will all be eligible for allocation to an analysis visit. If two or more observations fall into the same visit window, the observation closest to the target day will be used in the analysis. If there is a tie, the later observation will be used. However, for a participant who discontinues from the study early prior to Week 68 visit window in Part 1 (similarly to Week 52 visit window in Part 2), if two or more observations fall in the same visit window prior to Week 68 in Part 1 (similarly to Week 52 in Part 2), then the latest observation (rather than the observation closest to the target day) within this visit window will be used in the analysis for that visit window.

The analysis visit windowing will be applied after intercurrent events (initation of prohibited medications or discontinuation of study treatment, whichever is earlier) have been accounted for, that is, to the pre-intercurrent-event data and to all data separately (Appendix 3).

Table 8. Analysis Visit Windows for Part 1

Visit Label	Target Day ^a	Window Definition
Baseline	Day 1	Last non-missing assessment on or before Day 1 and prior to first dose of investigational product (ie, etrasimod or placebo)
Week 4	Day 29	Day 2 to Day 42
Week 8	Day 57	Day 43 to Day 70
Week 12	Day 85	Day 71 to Day 98
Week 16 ^b	Day 113	Day 99 to [Treatment Switch Day ^c or Day 126, whichever is smaller]
Week 20	Day 141	[Treatment Switch Day ^c +1 or Day 127, whichever is smaller] to Day 154
Week 24	Day 169	Day 155 to Day 196
Week 32	Day 225	Day 197 to Day 252
Week 40	Day 281	Day 253 to Day 322
Week 52	Day 365	Day 323 to Day 420
Week 68	Day 477	≥ Day 421

a. Target day is equal to the target week \times 7 days + 1 day.

b. All data collected on Week 16 visit, first open-label dose day (treatment switch day), will be included in ≤ Week 16 except for AE data, which will be included in ≥ Week 20. Any new treatment-emergent AE occurred on the day of first open-label dose (treatment switch day) will be included in ≥ Week 20.

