c. Day of first open-label dose at Week 16 = Treatment switch day (ie, treatment switch day = treatment switch date – date of the first dose +1), where treatment switch date is taken from the Treatment Dosing CRF, as the start date in the first entry of the Treatment Dosing log for the period of Week 16 to Week 20.

Note that the upper limit of the Week 16 visit window and the lower limit of the Week 20 visit window are defined uniquely for each of the participants in the study regardless of which treatment group the participants are randomized to.

If treatment switch day (ie, day of first open-label etrasimod dose) falls between Day 99 and Day 126, then the upper limit of the Week 16 visit window is the smaller of treatment switch day or Day 126, and the lower limit of the Week 20 visit window is the smaller of treatment switch day+1 or Day 127.

In the unlikely case if treatment switch day < Day 99, > Day126, or missing (eg, discontinuation of study treatment or study prior to Week 16), then the upper limit of the Week 16 visit window will be set to Day 126 and the lower limit of the Week 20 visit window will be set to Day 127.

Table 9. Analysis Visit Windows for Part 2

Visit Label	Target Day ^a	Window Definition
Baseline	Day 1	Last non-missing assessment on or before Day 1 and prior to first dose of etrasimod
Week 4	Day 29	Day 2 to Day 42
Week 8	Day 57	Day 43 to Day 84
Week 16	Day 113	Day 85 to Day 140
Week 24	Day 169	Day 141 to Day 210
Week 36	Day 253	Day 211 to Day 280
Week 44	Day 309	Day 281 to Day 336
Week 52	Day 365	≥ Day 337

a. Target day is equal to the target week \times 7 days + 1 day.

For safety data collected for participants who complete the 2-week and 4-week follow-up visits (Weeks 70 and 72 in Part 1 OLE, Weeks 54 and 56 in Part 2 OL Safety phase), available safety data will be summarized for these nominal visits.

For 12-Lead ECG collected on Day 1 during first-dose cardiac monitoring, the labels for timepoints can be "Day 1 Predose", "Day 1 1HR Postdose" to "Day 1 4HR Postdose".

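### Part 2 response rates at Weeks 36, 44 and 52 describe only Week 16 EASI-50 achievers still attending, and off-drug follow-up values can enter the Week 24 window

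*SAP*

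**What the plan says.** SAP 5.3 sets the Part 2 rule for binary efficacy: "Missing binary efficacy endpoints in Part 2 OL Safety phase will not be imputed as non-response, only observed values will be summarized". SAP 6.2.4 and Table 7 repeat it, and SAP 5.2 makes the evaluable participants the denominator of descriptive response rates. In Part 1 OLE, by contrast, SAP 5.3 and 6.2.4 set a missing binary response to non-response (MR=NR).

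Both parts have an EASI-50 stopping rule. Protocol 7.1.5 stops "Participants who do not meet EASI-50 criteria at Week 32 in Part 1 (Week 16 of OLE) or at Week 16 of Part 2", and these participants then "complete Early Termination procedures, and then complete the 2- week (SFU 1) and 4-week (SFU 2) follow-up visits". The Part 2 schedule (Protocol 1.3.3) agrees: "Participants who do not meet the pre-specified continuation criteria (EASI-50) will be discontinued at Week 16 and will complete ET visit procedures". In that schedule the row "EASI, IGA, BSA affected by AD" is marked at ET and at SFU 2, but not at SFU 1.

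On windowing, SAP Appendix 2.1 says: "Observations from all visits including scheduled, unscheduled and early termination visits will all be eligible for allocation to an analysis visit". If several values fall in one window, the one closest to the target day is used. The exception is a participant who leaves the study early: "then the latest observation (rather than the observation closest to the target day) within this visit window will be used in the analysis". Table 9 sets the Part 2 Week 16 window at "Day 85 to Day 140", Week 24 at Day 141-210, and opens Week 36 at Day 211. SAP 5.3 also says that Part 2 uses all observed data regardless of intercurrent events.

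**The concern.** The Part 2 endpoints are written as proportions of participants at all scheduled timepoints, with no condition on earlier response. The planned calculation imposes one. This is not ordinary dropout: a protocol rule based on response removes participants, and the observed-case denominator then leaves them out. A table of response by visit can rise after Week 16 although no participant has improved. The percentage and its confidence interval would describe a selected group without saying so.

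Part 1 OLE faces the same kind of rule at Week 32 and answers it with MR=NR. The SAP gives no reason for treating Part 2 differently. In Part 2 the observed-case summary is the only efficacy result planned.

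A second matter is that efficacy values are collected after drug is stopped, and no on-treatment cut-off applies in Part 2. Such values may be placed in the Week 24 window, and possibly in the Week 16 window.

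**Working it through.** The documents give no Part 2 response rate or dropout rate, so there is no figure of the plan to reproduce. The check is date arithmetic followed by a ratio.

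**Dates**

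- Week 16 visit: Day 113 ± 5, so Day 108-118 (Protocol 1.3.3).
- Last dose: assumed to be on the visit day or the day before, so Day 107-118.
- SFU 2: last dose + 28 ± 3 days. Earliest 107 + 25 = Day 132; latest 118 + 31 = Day 149.
- ET: within 1 week of last dose, so at the latest 118 + 7 = Day 125, inside the Week 16 window.
- The Week 36 window opens on Day 211. No scheduled EASI or IGA of a participant stopped at Week 16 can reach Week 36, 44 or 52.

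**Where SFU 2 lands.** There are 11 visit days × 2 last-dose options × 7 SFU 2 days = 154 combinations. SFU 2 falls on or before Day 140 in 35 of 77 (last dose on the visit day) and 42 of 77 (day before), so in 77 of 154. The other 77 fall on Day 141-149, in the Week 24 window. At nominal timing SFU 2 is 113 + 28 = Day 141 or 112 + 28 = Day 140, the boundary itself. These are counts of permitted dates, not probabilities.

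**Which Week 16 value is used.**

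- If the stop counts as leaving the study, the latest value in the window is taken. An SFU 2 on Day 132-140 then replaces the decision value; if SFU 2 is later, an ET held on a separate day replaces it. A stopped participant is by definition an EASI-75 and EASI-90 non-responder at the decision visit, so replacement can only leave or raise those two rates.
- If it counts only as stopping treatment, the closest value is taken. The Week 16 visit is at most 5 days from Day 113, and an SFU 2 on Day 132-140 is 19 to 27 days away. The decision value stays unless a separate-day ET happens to be closer to Day 113.

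**Size at Weeks 36-52.** Let f be the share stopped at Week 16, with no other loss and stopped participants counted as non-responders. Then all-treated rate = observed-case rate × (1 - f), and the ratio is 1/(1 - f). Since f is not in the documents, these are assumptions:

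| f | stopped of 340 | ratio |
|---|---|---|
| 20% | 68 | 1.25 |
| 35% | 119 | 1.54 |
| 50% | 170 | 2.00 |

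A 10% relative overstatement needs f = 1 - 1/1.10 = 9.1%, or 31 of 340.

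**Apparent rise from selection alone.** Assume f = 30% (102 stopped, 238 left) and the same 143 EASI-75 responders throughout. Week 16 would show 143/340 = 42% and Week 36 would show 143/238 = 60%.

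**If stopped participants were not all non-responders.** If they would respond at rate q and the observed-case rate is r, the excess is f(r - q). With r = 60% and f = 30%, the all-treated rate is 42% at q = 0, 45% at q = 10% and 48% at q = 20%.

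**The case against.** The SAP discloses its choice. It says openly that only observed values are summarised, and it states the denominator and tabulates N and n. Disposition (SAP 6.4.2) and treatment-duration categories (Table 5) will show attrition around Week 16. Part 2 is a supplementary safety database, its efficacy endpoints are exploratory, and no efficacy estimand is defined. All of this stands and keeps the priority low. It does not supply a label on the percentage and interval, or a second summary.

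It can also be said that the overstatement is partly one of definition. Participants who leave may use other treatments (Protocol 2.3.1), so their later status is unknown rather than known non-response. That is fair. The direction still holds for any later response rate below that of the retained participants.

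A reader might infer that off-drug SFU 2 values always replace the Week 16 decision value. The documents do not support that. The latest-value rule covers participants who leave the study early, whereas Protocol 7.1 and 7.1.5 treat a lack-of-efficacy stop as the end of study intervention and keep the participant for follow-up. On the other side, Protocol 7.2 lists lack of efficacy among reasons for leaving the study, and SAP 2.3 says only that non-responders are discontinued. The text is ambiguous.

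Appendix 2.1 does not name SFU visits. It does admit all visits, SFU 2 is scheduled with EASI and IGA, and its nominal-visit sentence for follow-up covers safety data only. Entry into Week 24 therefore stands on either reading of the study-discontinuation rule. It also returns some stopped participants to that denominator, which works against an overstatement at Week 24.

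**Conclusion.** The selection point holds: as planned, the Part 2 EASI-75, EASI-90 and IGA 0/1 rates at Weeks 36, 44 and 52 apply to Week 16 EASI-50 achievers still attending. They exceed the all-treated rate whenever someone is stopped, there are responders, and stopped participants count as non-responders. The factor 1/(1 - f) assumes no other dropout, and every value of f shown is an assumption.

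Entry of off-drug SFU 2 values on Day 141-149 into the Week 24 window follows from the windowing text. Replacement of the Week 16 value by SFU 2 is conditional on a lack-of-efficacy stop being read as leaving the study early; it is a gap to close, not an established error. The finding does not touch the safety objective of Part 2 or the Part 1 efficacy analysis.

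**What to change.** Keep the observed-case tables. Label rates after Week 16 as conditional on continuing past the EASI-50 rule, and report the number stopped at Week 16.

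In SAP 5.3, 6.2.4 and Table 7, add one summary of EASI-75, EASI-90 and IGA 0/1 over all treated Part 2 participants. Count missing values as non-response, and likewise all values after permanent treatment discontinuation for any reason. State the denominator explicitly, because SAP 4.1 defines the FAS by randomization and Part 2 is not randomized.

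In Appendix 2.1, state that for participants stopped at Week 16 the Week 16 analysis uses the assessment on which the EASI-50 decision was made. State also that SFU 2 efficacy values are reported as a nominal follow-up visit and are not windowed to Week 16 or Week 24.

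The cost is SAP wording and one extra set of descriptive tables, with no new data. The added long-term rates will be less favourable. They will also count visits missed for unrelated reasons as non-response, for example emergency telehealth visits at Weeks 8, 24 and 44, where Protocol 8.1.2 says IGA and EASI should not be done. That is the reason to keep both sets of tables.

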6. ANALYSES AND SUMMARIES

6.1. Primary Endpoint

6.1.1. Primary Analysis

The IGA response at Week 16 is the primary efficacy endpoint in Part 1 DB phase. The analysis of the primary endpoint will be based on Estimand E1 accounting for the intercurrent events using the FAS analyzed for participants with baseline IGA ≥2 (Section 4.1, Appendix 3). This corresponds to the primary estimand including only the preintercurrent-event data (Appendix 3). For the primary analysis, the normal approximation for the difference in binomial proportions adjusting for the actual stratification factor of baseline IGA (3 vs 4) via the CMH approach (Section 5.2.1.1) will be used. The baseline IGA from

the clinical database will be used as the actual stratification factor (Section 3.4.1). This CMH approach will be used to estimate the treatment difference in response rates of etrasimod 2 mg QD versus placebo and to generate 95% CI for the IGA response rate difference at Week 16 along with the 2-sided p-value (Section 5.2.1.1). Missing values will be handled by setting the IGA response value to non-response, MR=NR (Section 5.3). This is the primary analysis for IGA response at Week 16.

Analysis of IGA response at other visits prior to Week 16 (ie, exploratory endpoints) will also be analyzed using the same method based on the Estimand E1 including only the pre-intercurrent-event data on the FAS analyzed for participants with baseline IGA \geq 2.

6.1.2. Supportive Analysis

A supportive analysis will be conducted for the primary efficacy endpoint of IGA response at Week 16 based on Estimand E1a without regard to intercurrent events using the FAS analyzed for participants with baseline IGA ≥2 (Section 2.2.3, Appendix 3). This corresponds to the supportive estimand including all data (Appendix 3). For this supportive analysis, the same normal approximation for the difference in binomial proportions adjusting for the actual stratification factor of baseline IGA (3 vs 4) via the CMH approach (Section 5.2.1.1) will be used. The baseline IGA from the clinical database will be used as the actual stratification factor (Section 3.4.1). This CMH approach will be used to support the primary analysis of estimating the treatment difference in response rates of etrasimod 2 mg QD versus placebo and to generate 95% CI for the IGA response rate difference at Week 16 along with the 2-sided p-value. Missing values will be handled by setting the IGA response value to non-response, MR=NR (Section 5.3). This is the first supportive analysis for IGA response at Week 16.

Supportive analysis of IGA response at other visits prior to Week 16 will also be performed using the same method based on the Estimand E1a including all data on the FAS, all analyzing participants with baseline IGA ≥ 2 .

When there are discrepancies between actual stratification factor (baseline IGA of 3 vs 4) versus reported stratification factor from the randomization system, a sensitivity analysis for the IGA response at Week 16 and visits prior to Week 16 will be conducted using the normal approximation for the difference in binomial proportions adjusting for the reported (instead of actual) stratification factor of baseline IGA of 3 vs 4 via the CMH approach (Section 5.2.1.1). This includes the pre-intercurrent-event data under Estimand E1 on the FAS analyzed for participants with baseline IGA ≥2 (Section 3.4.1, Section 4.1, Appendix 3).

In addition, for the primary endpoint of IGA response at Week 16 under Estimand E1, a summary similar to the following will also be generated to assess the impact of intercurrent events on the estimates.

Table 4. IGA Response at Week 16 and Intercurrent Events

*	Etrasimod 2 mg QD	nd E1, MR=NR Placebo	
	(FAS N=xxx) [1]	(FAS N=xxx) [1]	
n (%)	(ITISTV XXX)	(ITISTV XXX)	
IGA Responders	xx (xx.xx)	xx (xx.xx)	
IGA Non-Responders	xx (xx.xx)	xx (xx.xx)	
1) Week 16 Completers with Observed Non-Response	xx (xx.xx)	xx (xx.xx)	
2) Week 16 Completers with Missing Response Set as Non-Response	xx (xx.xx)	xx (xx.xx)	
3) Initiation of Prohibited Medications Prior to Week 16 Visit (Earlier)	xx (xx.xx)	xx (xx.xx)	
4) Discontinued Study Treatment Due to Any Reason Prior to Week 16 Visit (Earlier)	xx (xx.xx)	xx (xx.xx)	
Reasons for Discontinuation of Study Treatment [2]			
Lack of Efficacy	xx (xx.xx)	xx (xx.xx)	
Adverse Event	xx (xx.xx)	xx (xx.xx)	
Death	xx (xx.xx)	xx (xx.xx)	
Lost to Follow-up	xx (xx.xx)	xx (xx.xx)	
Withdrawal by Subject	xx (xx.xx)	xx (xx.xx)	
Non-Compliance with Study Drug	xx (xx.xx)	xx (xx.xx)	
Protocol Deviation	xx (xx.xx)	xx (xx.xx)	
Pregnancy	xx (xx.xx)	xx (xx.xx)	
Physician Decision	xx (xx.xx)	xx (xx.xx)	
Medication Error without Associated Adverse	xx (xx.xx)	xx (xx.xx)	
Event			
Study Terminated by Sponsor	xx (xx.xx)	xx (xx.xx)	
Other	xx (xx.xx)	xx (xx.xx)	

^[1] N = number of participants in the FAS with Baseline IGA \geq 2. IGA response rates are calculated based on this as denominator.

